## 1.5 Study Design

This trial is a multi-center, randomized, double-blind, placebo-controlled, parallel-group study evaluating the efficacy and safety of 18 months of treatment with azeliragon relative to placebo conducted in approximately 800 mild AD patients who are on background standard of care (SoC). Patients will be randomly assigned to 1 dose level (5 mg/day plus SoC) or placebo plus SoC in a 1:1 randomization (approximately n=400/group).

This protocol describes two statistically independent studies with a common infrastructure. Statistical analysis for clinical efficacy will be analyzed as two identical separate studies (A-study and B-study). Analysis for safety and all secondary and exploratory endpoints will be analyzed for both the A and B study as a whole (i.e., the two studies combined).

A-study is conducted at multiple sites in the U.S and Canada.

B-study is conducted at multiple sites in the U.S., Canada, Ireland, UK, South Africa, New Zealand, and Australia.

The overall structure of the study includes the following periods:

**Screening period:** Screening procedures occur within 60 days of start of study drug administration, and they include obtaining informed consent and evaluations to determine eligibility for study participation.

**Baseline Study Period** (Day -7 — Day 1, pre-dose): Subjects will have baseline assessments for efficacy and safety measures, including vital signs, safety labs, adverse events, electrocardiography and concomitant medications, as well as imaging and PK/PD assessments.

**Treatment Period** (Day 1 — Month 18): Subjects are treated with double-blind study medication. Efficacy and safety measures are taken. Blood samples are taken and subjects have assessments for safety and PK.

**Follow-up period** (Month 21): Subjects return to the site for final safety assessments including vital signs, adverse events, electrocardiography and concomitant medications are taken. Blood draws are taken for safety evaluations and for pharmacokinetics evaluations.

## 1.6 Sample Size and Power Considerations

The protocol (Section 9.1) includes the following statements about sample size and power considerations:

The primary objective is to evaluate the effect of azeliragon plus SoC on cognition and functional outcome by comparing azeliragon plus SoC with placebo plus SoC. The co-primary endpoints are change from Baseline on the ADAS-cog total score at Month 18 and change from Baseline on the CDR-sb total score at Month 18. The study includes AD patients with mild disease as defined by having a baseline MMSE of 21 through 26.

This trial includes two independent sub-studies, each of which is supported by randomization independently, because randomization by investigative site is used. Each sub-study is powered using  $\alpha = 0.05$ .

Approximately 160 subjects (80 per treatment group) will be enrolled and participate in the FDG-PET sub-study. The sample size for this sub-study was selected empirically.

Sample size calculations are done to power each study (A-study and B-study) separately. It is anticipated that each A-study and B-study will randomize approximately  $N=400$ .

Assuming a standard deviation of the change from Baseline to Month 18 in ADAS-cog of 9 (based on Study TTP488-203), using  $\alpha = 0.05$ , a total sample size of 282 patients in balanced allocation (141 patients per group) provides at least 90% power to detect a difference between treatment groups of 3.5 (based on data from mild AD patients in Study TTP488-203) using a 2-sided, 2-sample t-test. Assuming a dropout rate of 20% or less, randomization of 354 patients provides adequate statistical power for this study to demonstrate superiority of azeliragon plus SoC over placebo plus SoC based on the ADAS-cog.

Assuming a standard deviation of the change from Baseline to Month 18 in CDR-sb of 2.4, using  $\alpha = 0.05$ , a total sample size of 304 patients in balanced allocation (152 patients per group) provides at least 90% power to detect a difference between treatment groups of 0.9 (based on data from mild AD patients in Study TTP488-203) using a 2-sided, 2-sample t-test. Assuming a dropout rate of 20% or less, randomization of 380 patients provides adequate statistical power for this study to demonstrate superiority of azeliragon plus SoC over placebo plus SoC based on CDR-sb.

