Upon completion of the study and locking the database, protocol-planned analysis of ADAS-cog data from 100% of subjects who were ongoing or who had completed 18 months at the time of study termination were performed. Analysis showed a beneficial effect of less cognitive decline in the 5 mg/day group compared to placebo at Month 18 ($\Delta = 3.1$, $p = 0.008$, analysis of covariance [ANCOVA] with multiple imputation). To confirm robustness of effect to statistical analysis procedures, this difference was found to be significant using other statistical models (ANCOVA with last observation carried forward [LOCF; $p = 0.03$] and generalized estimating equations [GEE; $p = 0.03$]).

Analysis was done to examine the impact of off-treatment data on analysis conclusions. Statistical analysis on ADAS-cog was performed using all available on-treatment data (“on treatment” defined as data collected within 45 days of the last

dose of study medication). Forty-five days was selected based on the long half-life of azeliragon (mean = 18 days in elderly participants) and the demonstration of measureable, appreciable concentrations during that time frame following the last dose. Mean changes in ADAS-cog show numerical active-placebo differences favoring the 5 mg/day dose group over time at all time points, with nominal significance at Month 18 (delta=2.7, p = 0.03).

The key secondary measure of CDR-sb at 18 months showed a numerical difference favoring 5 mg azeliragon over placebo CDR-sb (LOCF, delta = 0.73, p = 0.1)

The current study will enroll patients with mild Alzheimer's disease. Subgroup analyses of data in Study TTP488-203 based on baseline severity of AD (mild or moderate), planned in the protocol and SAP, showed a more pronounced benefit of treatment with azeliragon among subjects with mild disease (MMSE 21 or more). In patients with mild AD, the difference in ADAS-cog mean change from baseline at 18 months was 4.0 (p = 0.018). In addition, a nominally statistically significant difference in CDR-sb mean change from baseline was demonstrated (delta = 1, p = 0.02) when comparing azeliragon 5 mg + SoC with placebo + SoC at Month 18. Thus, in the Phase 2 trial statistically significant differences between azeliragon 5 mg/day and placebo on cognition and global performance (using USA FDA agreed upon Phase 3 registration measures of ADAS-cog and CDR-sb) have been demonstrated.

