9.1 SAMPLE SIZE DETERMINATION

The primary objective is to evaluate the effect of azeliragon plus SoC on cognition and functional outcome by comparing azeliragon plus SoC with placebo plus SoC. The co-primary endpoints are change from Baseline on the ADAS-cog total score at Month 18 and change from Baseline on the CDR-sb total score at Month 18. The study includes AD patients with mild disease as defined by having a baseline MMSE of 21 through 26.

This trial includes two independent sub-studies, each of which is supported by randomization independently, because randomization by investigative site is used. Each sub-study is powered using $\alpha = 0.05$.

Approximately 160 subjects (80 per treatment group) will be enrolled and participate in the FDG-PET sub-study at select sites in the United States and Canada. The sample size for this sub-study was selected empirically.

Sample size calculations are done to power each study (A-study and B-study) separately. It is anticipated that each A-study and B-study will randomize approximately N=400 each.

Assuming a standard deviation of the change from Baseline to Month 18 in ADAS-cog of 9 (based on Study TTP488-203), using $\alpha = 0.05$, a total sample size of 282 patients in balanced allocation (141 patients per group) provides at least 90% power to detect a difference between treatment groups of 3.5 (based on data from mild AD patients in Study TTP488-203) using a 2-sided, 2-sample t-test. Assuming a dropout rate of 20% or less, randomization of 354 patients provides adequate statistical power for this study to demonstrate superiority of azeliragon plus SoC over placebo plus SoC based on the ADAS-cog.

Assuming a standard deviation of the change from Baseline to Month 18 in CDR-sb of 2.4, using $\alpha = 0.05$, a total sample size of 304 patients in balanced allocation (152 patients per group) provides at least 90% power to detect a difference between treatment groups of 0.9 (based on data from mild AD patients in Study TTP488-203) using a 2-sided, 2-sample t-test. Assuming a dropout rate of 20% or less, randomization of 380 patients provides adequate statistical power for this study to demonstrate superiority of azeliragon plus SoC over placebo plus SoC based on CDR-sb.

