**STAGE 2:**

If and only if both hypothesis tests in A-study AD subjects and also B-study AD subjects for both co-primary variables (ADAS-cog and CDR-sb) have  $p < 0.05$  (i.e.,  $p < 0.05$  for ADAS-cog demonstrating statistical superiority of azeliragon 5 mg added to SoC versus placebo added to SoC and also  $p < 0.05$  for CDR-sb demonstrating statistical superiority of azeliragon 5 mg added to SoC versus placebo added to SoC (i.e., statistical significance of the test of the null hypothesis for each A-study and B-study independently), testing will proceed to the fifth set of hypotheses to the expansion of the population of subjects from A-study and B-study combined.

Consistent with the FDA draft Guidance for Industry: *Alzheimer's Disease: Developing Drugs for the Treatment of Early Stage Disease* (February, 2012), toward the goal of demonstrating disease modification, analysis of MRI data (hippocampal volume as the key secondary endpoint) will be done conditional on significance of the above-named hypothesis tests:

The next set of hypotheses to be tested is as follows:

- $H_{05}: \mu^{(MRI, \text{azeliragon, All})} = \mu^{(MRI, P, All)}$
- $H_{15}: \mu^{(MRI, \text{azeliragon, All})} \neq \mu^{(MRI, P, All)}$

where  $\mu^{(MRI, \text{azeliragon, All})}$  and  $\mu^{(MRI, P, All)}$  denote the true mean changes from Baseline at Month 18 on MRI volume measures for all AD azeliragon 5 mg/day and placebo groups, respectively.

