#### **5.2.1/5 Adjustments for multiplicity**

Multiplicity of the primary efficacy analyses is controlled by using a conditional sequence of hypotheses. The study will be considered to demonstrate statistical significance if the primary analysis has a resulting p-value less than 0.049 for both primary endpoints for both A-study and B-study. No other adjustment for multiplicity is required.

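### Does the plan overstate its power by giving 90% per endpoint and per sub-study when success needs all four tests?

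*SAP*

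**What the plan says.** Protocol 9.1, reproduced in SAP 1.6, plans each co-primary endpoint with a two-sided two-sample t-test at alpha 0.05:

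- ADAS-cog: difference 3.5, SD 9, 141 per group, inflated to 354 randomised.
- CDR-sb: difference 0.9, SD 2.4, 152 per group, inflated to 380 randomised. In the protocol's words, "Assuming a dropout rate of 20% or less, randomization of 380 patients provides adequate statistical power for this study", and the sentence goes on to limit this to CDR-sb. The SAP carries the same limit: "380 patients provides adequate statistical power for this study to demonstrate superiority of azeliragon plus SoC over placebo plus SoC based on CDR-sb".

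The scope is stated: "Sample size calculations are done to power each study (A-study and B-study) separately". About 400 are expected in each sub-study. The Protocol Summary gives greater exposure, not joint power, as the reason for planning 800 in all.

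The success rule is stricter than any one of these tests. SAP 5.2.1/5 requires a "p-value less than 0.049 for both primary endpoints for both A-study and B-study". SAP 2 opens the MRI test on the same condition: "If and only if both hypothesis tests in A-study AD subjects and also B-study AD subjects for both co-primary variables". The ranked secondary endpoints of Stage 3 come after that. SAP 1.5 describes the A-study and B-study as "two statistically independent studies with a common infrastructure".

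**The concern.** A reader who sees only 90% may take it as the chance that the trial succeeds if the drug works as planned. It is not. Two co-primary endpoints must both win, so power within a sub-study cannot exceed the lower of the two marginal powers. Two independent sub-studies must both win, so that figure is then squared. Neither document reports the result or gives the ADAS-cog/CDR-sb correlation needed to compute it.

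If the gap is large, a drug with the full planned effect could miss the success rule well over 10% of the time. A single miss among the four tests would also close formal testing of hippocampal volume and of the eight ranked secondary endpoints. Anyone reading a split result, such as three wins out of four, would want to know how likely that outcome was under the planning assumptions.

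**Working it through.** **Inputs.** From SAP 1.6 and protocol 9.1: differences 3.5 and 0.9, SDs 9 and 2.4, two-sided t-test, dropout up to 20%, about 400 per sub-study, 1:1 allocation. From SAP 5.2 and 5.2.1/5: alpha 0.049 at analysis. Assumed: correlation rho between the two test statistics, 0 to 0.7, with 1 as the upper bound.

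**Step 1: reproduce the plan's figures (alpha 0.05).** The normal approximation is n per group = 2(1.960 + 1.282)² × (SD/difference)².

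- ADAS-cog: 2 × 10.51 × (9/3.5)² = 139. The t-test minimum is 140; the plan uses 141, where power is 90.2%.
- CDR-sb: 2 × 10.51 × (2.4/0.9)² = 150. The t-test minimum is 151; the plan uses 152, where power is 90.3%.
- Inflation: 141/0.8 = 176.25, so 177 per group and 354 in all; 304/0.8 = 380.

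At alpha 0.049 the same sizes give 90.1% and 90.2%. The stated figures hold.

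**Step 2: marginal power at 400 per sub-study with 20% dropout.** There are 400 × 0.8 / 2 = 160 per group. The noncentrality is (difference/SD) × √(n/2):

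- ADAS-cog: (3.5/9) × √80 = 3.48, power 93.3%.
- CDR-sb: (0.9/2.4) × √80 = 3.35, power 91.6%.

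**Step 3: joint power.** Both endpoints in one sub-study: Φ₂(z₁, z₂; rho), where z₁ and z₂ are the normal quantiles of the two marginal powers. All four tests: the square of that.

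- rho 0: 0.9331 × 0.9155 = 0.854; squared, 0.730.
- rho 0.5: 0.870; squared, 0.757.
- rho 0.7: 0.881; squared, 0.776.
- rho 1: 0.9155; squared, 0.838.

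**Step 4: how far the answer moves (alpha 0.049, planned effects).**

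| Dropout | Evaluable per group | Four-test power, rho 0 to 0.7 |
|---|---|---|
| 20%, only 380 randomised | 152 | 68.9-74.3% |
| 20%, 400 randomised | 160 | 73.0-77.6% |
| 15% | 170 | 77.5-81.3% |
| 10% | 180 | 81.3-84.4% |
| none | 200 | 87.4-89.4% |

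The planned effects lie below the Phase 2 mild-subgroup results. Protocol 1.1.3 reports that "In patients with mild AD, the difference in ADAS-cog mean change from baseline at 18 months was 4.0", with a CDR-sb difference of 1. With 4.0 and 1.0 at 160 per group, four-test power is 87.9-89.7%.

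**Step 5: the test actually used.** The primary analysis (SAP 5.2.1) is an MMRM adjusted for baseline and stratum that also uses earlier visits of dropouts. The documents give no variance reduction for it. As an illustration, a 10% cut in residual variance at 160 per group gives 80-84% for the four tests, and a 20% cut gives 87-89%.

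**The case for a change.** The strongest case for a change is that the shortfall does not depend on the unknown correlation. At the full 20% dropout under the plan's own t-test, four-test power is at most 83.8%. Even one sub-study's two-endpoint criterion reaches only 85-88%, so pointing to separate powering does not rescue 90% for a sub-study. Under those conditions the rule is missed 22-27% of the time, against 7-8% for a single endpoint in a single sub-study. A few sentences would tell the reader so.

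All of that arithmetic stands, and the omission is real. What does not follow is that the plan is wrong. No sentence claims 90% for two endpoints or for four tests: each is limited to a named endpoint, and the section says the sub-studies are powered one at a time. That suits a design built for replication, with each sub-study locked, analysed and reported separately (protocol 11.1). The 73-78% range sits at the top of the allowed dropout, under a test less efficient than the primary one, and with a correlation that the reader has to supply.

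A smaller loose end is that protocol 9.5.5 gives the success threshold as 0.05, while protocol 9.5.2 and SAP 5.2.1/5 give 0.049. Protocol 9.0 says the SAP supersedes the protocol, so analysts will use 0.049. The choice moves four-test power by about 0.4 points.

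**Conclusion.** The concern does not call for a change. This is a gap in reporting, not an arithmetic error: the sizes and the 90% figures are correct for what they describe. Joint power is unstated, and anyone who needs it can derive it from the published inputs plus a correlation.

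Its size is about 73-78% for all four tests and 85-88% for one sub-study. This rests on 400 randomised per sub-study, 20% dropout, the planned effects and SDs, a completer t-test, and an assumed correlation of 0 to 0.7. Lower dropout, larger true effects or a more efficient MMRM would each raise it.

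Low joint power makes a false negative more likely; it does not inflate type I error or bias an estimate. The SAP was finalised after the final blind data review (SAP 1), so a new power figure would not serve to set the sample size. The success rule, alpha and analyses would read the same with or without it, and the conclusions remain sound if the plan is followed as written. A sponsor who wants to help readers of a split result could report the joint figures with their assumptions, but nothing depends on it.

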### **1.7 Early Stopping, Data Monitoring, and Interim Analysis**

There is no interim analysis in this study, except for medical and safety monitoring by the independent data monitoring committee (IDMC). This study has no plan for early stopping.

Except for the ongoing, blinded medical monitoring of accruing data and except for the ongoing review by the IDMC, no interim analysis is planned for this study. This study has no plan for interim analysis.

As a conservative measure, an alpha adjustment is applied to accommodate up to 10 analyses by the IDMC because the safety evaluation will include review of ADAS-cog data from the safety perspective.  $\alpha = 0.0001$  is apportioned to each of no more than 10 analyses by the IDMC that includes review of ADAS-cog data, blinded unless there is a data-driven need expressed by the IDMC to be unblinded.

With the exception of the IDMC, no unblinding is planned in this study for any reason other than emergency unblinding for medical imperatives.

It is emphasized that there is no interim analysis in this study for efficacy. The interim analyses described in this section refer to the analyses done by the IDMC for safety monitoring only.

## 1.8 Conformance to Regulatory Standards

An objective of this SAP is to comply with regulatory standards. The following guidance documents were specifically consulted in the preparation of this SAP:

- ICH E9: Statistical principles for clinical trials (September 1998); ICH and FDA
- ICH E9(R1): Estimands and sensitivity analysis in clinical trials (draft; 16 June 2017); ICH and FDA.
- ICH E14: Clinical evaluation of QT/QTc interval prolongation and proarrhythmic potential for non-antiarrhythmic drugs (October 2005); ICH and FDA
- E14 Q&A (R3) ICH guideline E14: the clinical evaluation of QT/QTc interval prolongation and proarrhythmic potential for non-antiarrhythmic drugs (R3)—questions and answers (26 January 2016); EMA
- Guideline on adjustment for baseline covariates in clinical trials (26 February 2015); EMA.
- Guideline on medicinal products for the treatment of Alzheimer’s disease and other dementias (24 July 2008); EMA.
- Good Review Practice: Statistical review template (30 July 2012). Office of Biostatistics; CDER; MAPP 6010.4
- Good Review Practice: Clinical review template (10 December 2010). Office of New Drugs; CDER; MAPP 6010.3
- Guidance: Providing clinical evidence of effectiveness for human drug and biological products (May 1998); CDER; CBER.
- Good Review Practice: Reviewer guidance: Conducting a clinical safety review of a new product application and preparing a report on the review (February 2005); CDER.
- Draft guidance: Developing drugs for the treatment of early stage disease (February 2013); CDER.
- Draft guidance: Adaptive design clinical trials for drugs and biologics (February 2010); CDER, CBER.
- Reflection paper on methodological issues in confirmatory clinical trials planned with an adaptive design (18 October 2007); EMA
- Draft guidance: Enrichment strategies for clinical trials to support approval of human drugs and biological products (December 2012); CDER, CBER, CDRH.
- Guidance: Drug-induced liver injury: premarketing clinical evaluation (July 2009); CDER, CBER.
- Guidance: Patient-reported outcome measures: Use in medical product development to support labeling claims (December 2009); CDER, CBER, CDRH.
- ICH and MSSO. (2017, September). MedDRA Introductory Guide Version 20.1.

The planned statistical analysis of this study is intended to comply with regulatory expectations and standards as depicted in the above-listed guidance documents.

## 1.9 Modifications from the Statistical Section of the Protocol

One modification from the Statistical Section of the Protocol is reflected in this SAP, based on agreement with the Neurology Products Division of the FDA:

- (1) Elimination of the use of Bazett's correction for QT-interval analysis, based on the recommendation depicted in ICH E14 Q&A R3 (dated 10 December 2015).

### **1.9.1 Modification: Elimination of Bazett's correction for QT-interval.**

The Q&A, Revision 3 ([10 December 2015](#)), published for ICH E14 indicates that Bazett's correction is not informative and discourages its use, and this guideline recommends Fridericia's correction.

## 2 Statistical Hypotheses

As depicted in the study protocol, a 2-stage conditional sequence of statistical hypothesis tests, will be used. The testing sequence will be as follows:

- Stage 1: Four concurrent analyses will be done:
  - A-study analysis of co-primary variables:
    - ADAS-cog is analyzed in A-study.
    - CDR-sb is analyzed in A-study
  - B-study analysis of co-primary variables:
    - ADAS-cog is analyzed in B-study.
    - CDR-sb is analyzed in B-study
- Stage 2: Conditional on statistical significance of both A-study and B-study in both co- primary variables, testing will continue:
  - MRI assessment is analyzed in the study (as a whole) Stage 2:
- Stage 3: Conditional on statistical significance in both stage 1 and stage 2 testing will continue:
- All other secondary endpoints will be evaluated in a hierarchical manner in the combined total of subjects in the 2 studies

For simplicity in notation, thresholds for significance are indicated as “ $p < 0.05$ ”; however, “0.05” is representative of the alpha allocated to the analysis. The overall study-wise alpha is 0.05, but particular analyses may have alpha less than 0.05.

### STAGE 1:

*Hypothesis tests for A-study are as follows:*

The first set of hypotheses to be tested is as follows:

- $H_{01}: \mu^{(\text{ADAS-cog, azeliragon, A-study})} = \mu^{(\text{ADAS-cog, P, A-study})}$
- $H_{11}: \mu^{(\text{ADAS-cog, azeliragon, A-study})} \neq \mu^{(\text{ADAS-cog, P, A-study})}$ ,

where  $\mu^{(\text{ADAS-cog, azeliragonTTP488, A-study})}$  and  $\mu^{(\text{ADAS-cog, P, A-study})}$  denote the true mean changes from Baseline at Month 18 on the ADAS-cog total score for the A-study azeliragon 5 mg/day added to SoC and placebo added to SoC groups, respectively.

The second set of hypotheses to be tested is as follows:

- $H_{02}: \mu^{(\text{CDR-sb, azeliragon, A-study})} = \mu^{(\text{CDR-sb, P, A-study})}$

- $H_{12}: \mu^{(\text{CDR-sb, azeliragon, A-study})} \neq \mu^{(\text{CDR-sb, P, A-study})}$ .

where  $\mu^{(\text{CDR-sb, azeliragon, A-study})}$  and  $\mu^{(\text{CDR-sb, P, A-study})}$  denote the true mean changes from Baseline at Month 18 on the CDR-sb score for the A-study azeliragon 5 mg/day and placebo groups, respectively.

